5.7. Analysis of Safety Data

The analysis of safety and tolerability will be performed on the SAF and SAF-maintenance for each study period, as defined in Section 3.3.

The safety analysis will be based on the reported AEs, clinical laboratory evaluations, physical examination, vital signs and spirometry.

Thresholds for treatment-emergent Potential Clinically Significant Values (PCSV) in laboratory variables and vital signs are defined in Section 10.3. Treatment-emergent PCSV is any PCSV developed or worsened in severity compared to the baseline during the treatment and follow-up period.

The time interval to detect any event or abnormality is between the first injection of study medication and EOS.

The summary of safety results will be presented for each study period by treatment received in the corresponding period. For safety variables/summaries involving baseline values, e.g., absolute change from baseline or shift table, study period specific baselines will be used. Summaries for pre-dosing period and up-dosing period will use the study baseline (i.e., the latest available valid measurement prior to the first dose of study drug in the study). Summaries for maintenance period and follow-up period will use study baseline and visit 16 baseline (i.e., the last available valid measurement prior to the first dose of study drug in the maintenance period), respectively.

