6.1. Definition of Baseline for Efficacy/Safety Variables

Unless otherwise specified, the study baseline assessment for all measurements will be the latest available valid measurement taken prior to the first administration of study drug. If any randomized subjects are not treated, the baseline will be the last value on or prior to the randomization. In addition, maintenance period baseline is defined as the last available valid measurement taken prior to the first administration of dupilumab/placebo during the maintenance period.

The following rules specify the determination of baseline by both date/time information:

- The date and time of first injection will be used to determine the baseline for the AE, lab, PK and ADA data.
- Only the date of first injection will be used to determine the baseline for other data expect AE, lab, PK and ADA data.

For the re-screened subjects, all data from the same subject will be used to derive baseline regardless if the data is from the screen-failure subject ID or enrolled subject ID.

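### SAP 5.7 as worded measures maintenance-period safety changes from the pre-study baseline, so abnormalities that began in up-dosing and persist count as emergent in maintenance

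*SAP*

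**What the plan says.** SAP 5.7 sets the rule for every safety summary that uses a baseline: "For safety variables/summaries involving baseline values, e.g., absolute change from baseline or shift table, study period specific baselines will be used". Pre-dosing and up-dosing take the study baseline, which is "the latest available valid measurement prior to the first dose of study drug in the study". For the two later periods the text reads "Summaries for maintenance period and follow-up period will use study baseline and visit 16 baseline", with the visit 16 baseline explained as "the last available valid measurement prior to the first dose of study drug in the maintenance period), respectively". Results are "presented for each study period by treatment received in the corresponding period".

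The same section calls a PCSV treatment-emergent if it appears or worsens relative to baseline during treatment or follow-up. Most limits in SAP 10.3 have the baseline value built in.

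SAP 6.1 adds that "maintenance period baseline is defined as the last available valid measurement taken prior to the first administration of dupilumab/placebo during the maintenance period". In substance this is the visit 16 baseline of 5.7. Protocol 11.5 has a single baseline, before the first dose.

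SAP 5 gives maintenance three columns: continuous placebo, dupilumab in up-dosing then placebo, and continuous dupilumab, all with AR101.

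**The concern.** The section announces period-specific baselines and then, on its plain wording, gives maintenance the same reference point as up-dosing. The baseline that 6.1 defines for maintenance goes only to follow-up.

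Maintenance is where dupilumab is continued or stopped at random, and safety and tolerability is a secondary objective. A maintenance safety table should show what changed after re-randomisation. Measured from a value taken 28 to 40 weeks earlier, its change, shift and PCSV entries combine what happened in up-dosing with what happened afterwards. For subjects who stopped dupilumab, an abnormality that began on the drug is reported as emergent in the period when they were receiving placebo.

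**Working it through.** **1. What the sentence can mean.** SAP 3.3 places in follow-up some subjects who never entered maintenance: those who did not reach 300 mg/day for two weeks, and those who stopped treatment during up-dosing. They have no first maintenance dose, so no visit 16 baseline as 5.7 defines it.

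| Reading | Maintenance baseline | Follow-up baseline | Usable for follow-up subjects who skipped maintenance? |
|---|---|---|---|
| Literal pairing | Study | Visit 16 | No |
| Both baselines for both periods | Both | Both | Study version only |
| The two baselines transposed | Visit 16 | Study | Yes, but contrary to the word order |

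**2. The literal rule applied to one subject.** The ALT limit in SAP 10.3 is above 3 and up to 5 × ULN, with baseline at or below 3 × ULN. Take a hypothetical subject at 1 × ULN before the study, 4 × ULN at visit 16 on dupilumab, and 4 × ULN at visit 19 after switching to placebo.

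- Study baseline: 4 is in range and 1 ≤ 3, so the value is flagged as emergent in maintenance.
- Visit 16 baseline: 4 is in range but 4 > 3, so it is not flagged.

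**3. What can carry over.** Only abnormalities measured again as abnormal after visit 16 count. Protocol Table 4 repeats hematology and chemistry at visits 19 and 22, and vital signs at every maintenance visit. Some carriers would have dosing interrupted: Protocol 8.3.2.2 lists ALT or AST from 3 to 5 × ULN. Others would not. The eosinophil PCSV limit is 0.5 Giga/L (and above ULN), while the interruption limit is 5000/µL, which is 5 Giga/L. Counts between the two can persist without interruption.

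**4. Expected number flagged with no new event.** The formula is n × u × p. Here n is the number who stop dupilumab, u the proportion acquiring a given PCSV in up-dosing, and p the proportion of these still abnormal in maintenance. From the documents, n is at most 104/2 = 52. The values of u (5% to 20%) and p (25% to 100%) are assumptions.

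- Low: 52 × 0.05 × 0.25 = 0.65 subjects (1.25%).
- Middle: 52 × 0.10 × 0.50 = 2.6 subjects (5%).
- High: 52 × 0.20 × 1.00 = 10.4 subjects (20%).
- Visit 16 baseline: 0 throughout.

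**5. Against continuous placebo.** Assume 80% of dupilumab and 70% of placebo subjects enter maintenance: 104 × 0.8 / 2 = 41.6 per former-dupilumab group, and 52 × 0.7 = 36.4 on placebo. With carried-in rates of 10% and 5%, the dupilumab-to-placebo column starts at 4.2 subjects and placebo at 1.8. At 5% and 2.5% the counts are 2.1 and 0.9; at 15% and 5%, 6.2 and 1.8. With 10% in both they are 4.2 and 3.6, and the percentages do not differ. Any excess therefore comes entirely from the assumed difference in up-dosing rates.

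**6. Continue versus stop.** Let both groups carry in proportion c, and let new-onset rates among the rest be a and b. The table shows c + (1 − c)a and c + (1 − c)b, so the difference becomes (1 − c)(b − a) and the ratio moves toward 1. For a = 5% and b = 10% (assumed; true ratio 2.0):

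- c = 1.25%: 11.1% against 6.2%, ratio 1.80.
- c = 10%: 19.0% against 14.5%, ratio 1.31.
- c = 20%: 28.0% against 24.0%, ratio 1.17.

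**The case against.** The strongest reply is that the wording is loose. SAP 5.3, 5.4, 5.12 and 5.13 use *respectively* to mean separately, with no one-to-one pairing. Read that way, 5.7 produces both periods against both baselines, which already supplies the table wanted here. This stands as a possible reading. It does not remove the problem: the literal pairing is the plain one, and neither it nor the two-baseline reading gives a complete rule for follow-up.

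A second reply is that the study baseline is legitimate. Protocol 11.5 has no other, and Protocol 11.4.4.1 treats up-dosing, maintenance and follow-up as one treatment-emergent period. Cumulative change since entry is worth reporting, so those tables should stay. But 5.7 says period-specific baselines will be used, and a cumulative table does not deliver that.

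Three stronger conclusions might be inferred, and the documents do not support them:

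- *Dupilumab abnormalities are pooled into placebo.* SAP 5 gives the switched subjects their own column, with the earlier dupilumab named in its label. Continuous placebo carries in only its own up-dosing abnormalities.
- *The randomised comparison is biased.* Continuing and stopping groups come from one arm by 1:1 re-randomisation, so carried-in abnormalities balance in expectation. What remains is dilution. The safety summaries at issue are descriptive (SAP 10.1), and SAP 5.6.3 plans no formal hypothesis for maintenance.
- *New abnormalities cannot be identified.* SAP 5.7.3 and 5.7.4 provide by-visit values and listings, so a reader can see whether an abnormality predates visit 16.

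**Conclusion.** The point holds as a drafting conflict with a real effect on the tables. On its plain reading, 5.7 contradicts its own period-specific rule and leaves the 6.1 maintenance baseline unused for maintenance. Maintenance change, shift and PCSV summaries would then count persistent up-dosing abnormalities as emergent. The continue-versus-stop contrast is diluted, and the descriptive comparison of the dupilumab-to-placebo group with continuous placebo mixes earlier dupilumab exposure with the maintenance effect.

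The size cannot be fixed from the documents. The 0.65 to 10.4 subjects rest on assumed acquisition and persistence rates and on all 104 dupilumab subjects entering maintenance. They make no allowance for carriers whose treatment was stopped. Primary efficacy is unaffected. This should be corrected before the maintenance tables are programmed.

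**What to change.** Reword SAP 5.7 to say three things:

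1. Maintenance change-from-baseline, shift and treatment-emergent PCSV summaries use the maintenance-period baseline of SAP 6.1. For vital signs and spirometry this should be the pre-challenge visit 16 value. Both challenge days precede the first maintenance injection (Protocol Table 4, footnote 1), so the last value before that injection could otherwise be a post-challenge one.
2. The study-baseline version of these tables is kept as additional output, for cumulative change.
3. The follow-up baseline is stated, including the one used for subjects who did not enter maintenance.

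The cost is a short text change and one extra set of maintenance tables. Visit 16 laboratory, vital-sign and spirometry data are already scheduled, and assessments are made before study drug is given, so no new data are needed.

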5.7.1. Adverse Events

The number and proportion of subjects reporting TEAEs will be summarized for pre-dosing period, up-dosing period, maintenance period and follow-up period separately, as described in Section 3.3.

AE incidence tables will be presented by treatment group for the SAF and SAF-maintenance as well as subgroups. Summary of TEAEs will present the number (n) and percentage (%) of subjects experiencing an TEAE by SOC, and PT, sorted by decreasing frequency of SOC and PT for the dupilumab treatment group in the pre-dosing period, dupilumab plus AR101 treatment group in the up-dosing period, and continuously on dupilumab plus AR101 treatment group in the maintenance period. Multiple occurrences of AEs of the same PT (or SOC) in the same subject will be counted only once for that PT (or SOC). For AE tables presenting severity, the worst severity will be chosen for subjects with multiple instances of the same event. The denominator for computation of percentage is the number of subjects in each treatment group for the corresponding analysis period as specified in Section 3.3.

An overall summary of TEAEs will be provided with number and proportions of subjects with any:

- TEAE
- Serious TEAE
- TEAE of special interest (AESI)

- TEAE/Serious TEAE leading to death
- TEAE/Serious TEAE leading to permanent treatment discontinuation
- TEAE/Serious TEAE of injection site reaction
- Study drug related TEAE/serious TEAE

Detailed summaries of TEAEs will include:

- TEAEs
 - TEAEs by SOC/PT
 - TEAEs by SOC/HLT/PT
 - TEAEs by PT
 - TEAEs by SOC/PT with incidence of $PT \ge 5\%$ in any treatment group
 - TEAEs by severity and by SOC/PT
 - Severe TEAEs by SOC/PT
 - TEAEs related to dupilumab/placebo as assessed by the investigator by SOC/PT
 - TEAEs related to AR101 as assessed by the investigator by SOC/PT
 - Severe TEAEs related to dupilumab/placebo as assessed by the investigator by SOC/PT
 - Severe TEAEs related to AR101 as assessed by the investigator by SOC/PT
 - TEAE of special interest
- Serious TEAEs:
 - Serious TEAEs by SOC/PT
 - Serious TEAEs related to dupilumab/placebo as assessed by the investigator by SOC/PT
 - Serious TEAEs related to AR101 as assessed by the investigator by SOC/PT
- TEAEs leading to permanent discontinuation of study treatment by SOC/PT
- Death by SOC/PT

Number and proportion of subjects reporting pre-treatment adverse events will be tabulated by SOC and PT.

Listing of TEAEs, serious TEAEs, and TEAEs resulting in death and study drug discontinuation will be generated. The following variables will be included in the listing:

- Subject ID
- Treatment group
- Study phase

CONFIDENTIAL

Page 45 of 86

- Age/sex/race
- System Organ Class (SOC)
- High Level Term (HLT)
- Preferred Term (PT)
- Verbatim Term
- AE start date and end date/ongoing (including both calendar days and study days)
- AE duration
- Relationship of AE to dupilumab/placebo: unrelated or related
- Relationship of AE to AR101: unrelated or related
- Action taken with dupilumab/placebo: Dose not changed, Drug interrupted, Drug withdrawn, Not applicable, or Unknown
- Action taken with AR101: Dose not changed, Dose reduced, Drug interrupted, Drug withdrawn, Not applicable, or Unknown
- Severity: mild, moderate, or severe
- Outcome: Fatal, Not recovered/not resolved, Recovered/resolved, Recovered/resolved with sequelae, Recovering/resolving, or Unknown.
- Impact by COVID-19 pandemic: Yes or No

In addition, summary of adverse events will be categorized by the status of impact by COVID-19 pandemic. For subjects who were impacted by COVID-19 pandemic, the summary of adverse events by study period will include overall summary of adverse event, TEAEs by SOC/PT, serious TEAEs by SOC/PT (if applicable), TEAEs of special interest (if applicable), TEAEs leading to discontinuation of study treatment by SOC/PT (if applicable). The summary of adverse events by study period for subjects who were not impacted by COVID-19 pandemic will be summarized similarly. The summary of adverse events will be performed for pre-, during-, and post-COVID-19 periods for subjects impacted by COVID-19, if applicable.

5.7.2. Analysis of Adverse Events of Special Interest

The adverse events of special interest (AESI) for dupilumab and AR101 will be summarized by AESI category (see Section 10.4) and HLT/PT, respectively.

The time to first AESIs (TEAE by category) or TEAE leading to permanent treatment discontinuation will be assessed by Kaplan-Meier estimates. Kaplan-Meier plots will be provided. In order to detect any safety signals, the hazard ratio (HR) will be provided together with the corresponding 95% confidence interval (CI) for the selected adverse events. Hazard ratios will be calculated using a Cox model including factors of treatment group, and randomization strata. The time is defined as the date of first event – the date of first dose + 1. Subjects without an event will be censored at the end of each study period. Graphs of cumulative incidence rate over time will be presented by treatment group.

The number of anaphylactic reactions, the number and percent of subjects experiencing an anaphylactic reaction, the number and percent of subjects experiencing an anaphylactic reaction by maximum severity using the Muraro Grading Scale (Muraro 2007), the number of subjects experiencing an anaphylactic reaction was an SAE, the number of subjects experiencing an anaphylactic reaction that required use of epinephrine will be summarized for each study period and during DBPCFCs.

5.7.3. Clinical Laboratory Measurements

Laboratory measurements include clinical chemistry, hematology and urinalysis results, and will be converted to standard international units. Summaries of laboratory variables will include:

- Descriptive statistics of laboratory result and change from baseline by visit
- The number (n) and percentage (%) of subjects with treatment-emergent PCSVs. This summary will be provided based on all subjects in the SAF as well as in the subgroup of SAF subjects who did not meet the PCSV criterion at baseline
- Shift tables based on baseline normal/abnormal and other tabular and graphical methods may be used to present the results for parameters of interest

Listing of all laboratory parameters normal range, abnormal flag, treatment-emergent PCSV by subject, visit and the status of impact by COVID-19 pandemic will be provided.

In addition, summaries of laboratory variables will be performed for subjects who were impacted by COVID-19 pandemic and not impacted by COVID-19 pandemic in each study period, respectively. The summaries will be performed for pre-, during-, and post-COVID-19 periods for subjects impacted by COVID-19, if applicable.

5.7.4. Analysis of Vital Signs

Summaries of vital sign variables excluding post-dose measurements at AR101 up-dosing visit and measurements at DBPCFCs will include:

- Descriptive statistics of vital sign variables and change from baseline by visit
- The number (n) and percentage (%) of subjects with treatment-emergent PCSV
- Shift tables based on baseline normal/abnormal and other tabular and graphical methods may be used to present the results for parameters of interest

Summaries of vital sign variables at DBPCFCs of peanut protein will include:

- Descriptive statistics of vital sign variables and change from pre-dose by challenge level
- Shift tables based on baseline normal/abnormal and other tabular and graphical methods may be used to present the results for parameters of interest

Listings of vital sign will be provided with flags indicating the treatment-emergent PCSVs and the status of impact by COVID-19 pandemic.

In addition, summaries of vital signs will be performed for subjects who were impacted by COVID-19 pandemic and not impacted by COVID-19 pandemic in each study period, respectively. The summaries will be performed for pre-, during-, and post-COVID-19 period for subjects impacted by COVID-19, if applicable.

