APPENDIX 3. CRITERIA FOR SUSPECTED DIAGNOSIS AND SEVERITY GRADING OF ANAPHYLAXIS

Anaphylaxis is likely when any one of the 3 following sets of criteria is fulfilled:

1. Acute onset of an illness (min to h) with involvement of:

- Skin/mucosal tissue (eg, generalized hives, itch or flush, swollen lips/tongue/uvula) AND
- Airway compromise (eg, dyspnea, stridor, wheeze/ bronchospasm, hypoxia, reduced PEF) AND/OR
- Reduced BP or associated symptoms (eg, hypotonia, syncope, incontinence)

2. Two or more of the following that occur rapidly after exposure to the allergen (min to h):

- Skin/mucosal tissue (eg, generalized hives, itch/flush, swollen lips/tongue/uvula)
- Airway compromise (eg, dyspnea, stridor wheeze/bronchospasm, hypoxia, reduced PEF)
- Reduced BP or associated symptoms (eg, hypotonia, syncope, incontinence)
- Persistent GI symptoms (eg, nausea, vomiting, crampy abdominal pain)

3. Reduced BP after exposure to the allergen (min to h):

- Infants and Children: low systolic BP (age-specific) or > 30% drop in systolic BP*
- Adults: systolic BP < 90 mm Hg or > 30% drop from their baseline

[figure not shown]
* Low systolic BP for children is defined as < 70 mmHg from 1 month to 1 year; less than (70 mmHg + [2 x age]) from 1 to 10 years; and < 90 mmHg from age 11 to 17 years.

Note: Isolated skin or mucosal lesions following the ingestion of a food constitute a "food-induced allergic reaction".

Criteria for Severity Grading (Muraro 2007)

Staging System of Severity of Anaphylaxis					
Stage	Defined By				
1. Mild (skin & subcutaneous tissues, GI, &/or mild respiratory)	Flushing, urticaria, periorbital or facial angioedema; mild dyspnea, wheeze, or upper respiratory symptoms; mild abdominal pain and/or emesis				
2. Moderate (mild symptoms + features suggesting moderate respiratory, cardiovascular, or GI symptoms)	Marked dysphagia, hoarseness and/or stridor; shortness of breath, wheezing & retractions; crampy abdominal pain, recurrent vomiting, and/or diarrhea; and/or mild dizziness				
3. Severe (hypoxia, hypotension, or neurological compromise)	Cyanosis or $\text{SpO}_2 \leq 92\%$ at any stage, hypotension, confusion, collapse, loss of consciousness; or incontinence				

APPENDIX 4. SCHEMATIC FOR AR101 INITIAL DOSE ESCALATION DAY PERFORMED IN-CLINIC AT WEEK 4

[figure not shown]

Regeneron Pharmaceuticals, Inc.

CONFIDENTIAL

Page 116 of 118

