4.6.4. Vital Signs

Vital signs, including temperature, sitting blood pressure, pulse, and respiration rate will be collected pre-dose at screening visit 1, screening visit 1a, every scheduled visit and the unscheduled visit or ET visit. During the DBPCFC, IDE and up-dosing, vital signs will be monitored every 15 to 30 minutes. For post-dose monitoring, only pulse and blood pressure need to be taken as part of safety monitoring.

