| Visit 22 (Week 52 to 64, V16 + 24 weeks) | Visit 16 TD + 168 days | [Visit 22 TD – 13 days, Visit 22 TD + 14 days] |
| Following window | ws apply to subjects who entered | follow-up period |
| Visit 23 (V16 + 28 weeks) | Target Day (TD) at last visit in pre-dosing/up- dosing/maintenance period ^e + 28 days | [Visit 23 TD – 13 days, Visit 23 TD + 14 days] |
| Visit 24 (V16 + 32 weeks) | Target Day (TD) at last visit in pre-dosing/up- dosing/maintenance period + 56 days | [Visit 24 TD – 13 days, Visit 24 TD + 14 days] |
| Visit 25 (Week 64 to 76, V16 + 36 weeks) | Target Day (TD) at last visit in pre-dosing/up- dosing/maintenance period + 84 days | ≥ Visit 24 TD + 14 days |

^a Study day is calculated relative to the date of first study drug injection.

^b Visit 15a – 15f are optional visits in order to reach 300 mg/day AR101 for at least two weeks. Subjects may reach 300 mg/day AR101 for at least two weeks at any of the optional visits.

^c The last visit during up-dosing period could be any of visit 15, 15a, 15b, 15c, 15d, 15e, or 15f.

^dVisit 16 target day (TD) is defined as target day at last visit during up-dosing period + 14 days.

^e The target day at last visit in pre-dosing/up-dosing/maintenance period could be any of the following visit: 1) visit 15 during up-dosing period; 2) ET visit during up-dosing period; 3) visit 22 during maintenance period; 4) ET visit during maintenance period.

In general, the following order will be used to select the record for analysis at given visit:

- 4. Scheduled visit
- 5. ET or end of study (EOS), whichever comes first if scheduled visit not available
- 6. Unscheduled visit if both scheduled visit and ET/EOT/EOS are not available

For the multiple measurements of the same test in the same window, the following rules will be used to select the analysis value:

- If multiple valid values of a variable within an analysis visit window, the closest from the target study day will be selected.
- If the difference is a tie, the value after the targeted study day will be selected.
- If multiple available values of a variable exist within a same day, then the first value of the day will be selected.

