| Eosinophils (EOS) | (>0.5 Giga/L and >ULN) and (\leq 0.5 Giga/L or \leq ULN at baseline) | Harrison- Principles of internal Medicine 17th Ed., 2008. |
| Hemoglobin (HGB) | ${<}100$ g/L and ${\geq}100$ g/L at baseline or any decrease ${\geq}~20$ g/L | Two criteria are independent |
| | >200 g/L and \leq 200 g/L at baseline | |
| Hematocrit (HCT) | $<0.37 \text{ v/v} \text{ and } \ge 0.37 \text{ v/v} \text{ at baseline for Male;}$ | Two criteria are independent |
| | $<0.33 \text{ v/v}$ and $\ge 0.33 \text{ v/v}$ at baseline for Female | |
| | >0.52 v/v and ≤0.52 v/v at baseline for Male; >0.47 v/v and ≤0.47 v/v at baseline for Female | |
| Platelets (PLAT) | <100 Giga/L and ≥100 Giga/L at baseline >700 Giga/L and ≤700 Giga/L at baseline | International Consensus meeting on drug- induced blood cytopenias, 1991. Two independent criteria |
| Urinalysis | | |
| pH (PH) | <5 or >7 | |
| Ketones (KETONES) Ketonuria | Presence and absence at baseline | Semi-quantitative methods |
| Ketonuna | | |

| Glucose (GLUC) Glycosuria | Presence and absence at baseline | Semi-quantitative methods |
|---|--|---|
| Erythrocytes (RBC) Microscopic Hematuria | > 5 RBCs/ HPF and ≤5 RBCs/ HPF at baseline | Semi-quantitative methods |
| Protein (PROT) Proteinuria | \geq 1+ and <1 at baseline | Semi-quantitative methods, $\geq 1+$ means concentration ≥ 30 mg/dL |
| Vital Signs | | |
| HR | ≤50 bpm and decrease from baseline ≥20 bpm ≥120 bpm and increase from baseline≥20 bpm | To be applied for all positions (including missing) except STANDING. |
| SBP | ≤90 mmHg and decrease from baseline ≥20mmHg ≥119 mmHg and increase from baseline ≥20 mmHg. | |
| DBP | ≤54 mmHg and decrease from baseline ≥10 mmHg ≥78 mmHg and increase from baseline ≥10 mmHg | |
| Temperature | Rectal, Tympanic: >100.4 °F/38.0 °C Oral: >99.5 °F/37.5 °C Axillary or skink infrared (temporal): >37.2 °C | |
| Respiratory rate | < 12 per minute and ≥12 per minute at baseline >20 per minute and ≤20 per minute at baseline | |
| Weight | ≥5 % weight loss from baseline ≥5 % weight gain from baseline | Based on identification of trends in the child's growth with a series of visits WHO Multicentre Reference Study Group, 2006; Center for Disease Control. Growth chart 2007. |

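### Post-dose pulse and blood pressure at AR101 up-dosing visits are only listed: SAP 5.7.4 leaves them out of every vital-sign summary and the only vital-sign PCSV count, which is narrower than the protocol and not declared.

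*SAP*

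**What the plan says.** SAP 4.6.4 sets the collection: "During the DBPCFC, IDE and up-dosing, vital signs will be monitored every 15 to 30 minutes". After a dose only pulse and blood pressure are needed, and the stated purpose is safety monitoring.

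SAP 5.7.4 then plans three outputs.

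- A main block, introduced by "Summaries of vital sign variables excluding post-dose measurements at AR101 up-dosing visit and measurements at DBPCFCs will include". It contains by-visit descriptive statistics, shift tables and "The number (n) and percentage (%) of subjects with treatment-emergent PCSV".
- A food-challenge block, introduced by "Summaries of vital sign variables at DBPCFCs of peanut protein will include". It contains change from pre-dose by challenge level and shift tables.
- Listings: "Listings of vital sign will be provided with flags indicating the treatment-emergent PCSVs and the status of impact by COVID-19 pandemic". The exclusion is not repeated here.

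Protocol 11.4.4.2 plans the number and percentage of subjects with a treatment-emergent PCSV for each vital sign. It leaves the criteria to the SAP and excludes no readings. SAP 5.7 defines treatment-emergent PCSV as one that develops or worsens relative to baseline at any time during treatment or follow-up. SAP 1.2.3, which lists the changes from the protocol's statistical section, says nothing about vital signs.

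**The concern.** Whether adding dupilumab makes AR101 safer and better tolerated is a secondary objective, and the protocol's rationale is largely about up-dosing. The post-dose readings at up-dosing visits are clinic-measured, taken on a common schedule in both arms, and do not depend on anyone deciding that an event occurred. If they enter no summary, the vital-sign tables for those visits show pre-dose values and cannot show what followed the dose. A between-arm difference in measured falls could then be found only by reading listings line by line. This matters more because SAP 1.2.3 removes the e-diary tolerability objective for low diary compliance and replaces it with exploratory endpoints.

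**Working it through.** The plan gives no figure to reproduce. The check is which readings enter which output, followed by a rough size.

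**1. Trace the readings through SAP 5.7.4.**

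- Main block: post-dose readings at up-dosing visits are out by its opening words, so they are also outside the PCSV count that sits under it.
- Food-challenge block: its scope is peanut challenges, so it does not bring them back. It has no PCSV count either.
- Listings: no exclusion is stated, so the readings and their PCSV flags appear there.

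Result: listed, not summarized and not counted.

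**2. Compare with the governing text.** Protocol 11.4.4.2 counts PCSVs for each vital sign with no exclusion. SAP 5.7 counts any PCSV that develops during treatment or follow-up. SAP 5.7.4 is narrower than both, and SAP 1.2.3 does not record the difference.

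**3. Week 4 IDED.** The exclusion names the AR101 up-dosing visit. SAP 4.6.4 names initial escalation and up-dosing as separate occasions, but SAP 3.3 starts the up-dosing period on the IDED date. Either reading is possible. SAP 6.4 says "If multiple available values of a variable exist within a same day, then the first value of the day will be selected", which would keep IDED post-dose values out of by-visit tables. That section governs by-visit analyses, however, and a PCSV count under SAP 5.7 is not limited to one value per visit. The plan does not settle whether IDED post-dose readings are counted.

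**4. Amount of data.** Inputs:

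- Dose increases, Protocol Table 2: 6, 12, 20, 40, 80, 120, 160, 200, 240 and 300 mg (weeks 6 to 24), which is 10.
- Observation after each increase, Protocol 6.1.1.2: at least 2 hours (120 minutes).
- Reading interval, SAP 4.6.4: 15 to 30 minutes.
- Subjects, SAP 2.1: about 156.

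Readings per visit: 120 / 30 = 4 to 120 / 15 = 8.
Per subject completing the schedule: 10 × 4 = 40 to 10 × 8 = 80.
All subjects: 156 × 40 = 6,240 to 156 × 80 = 12,480.

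The totals assume that all 156 subjects complete every step, so they are high on that count. IDED readings are not included.

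**5. Why a new table must name its low-systolic flag.** SAP 10.3 uses "≤90 mmHg and decrease from baseline ≥20mmHg". Protocol Appendix 3 uses, for children, "less than (70 mmHg + [2 x age]) from 1 to 10 years; and < 90 mmHg from age 11 to 17 years", or a fall of more than 30%. At age 6 the Appendix 3 limit is 70 + 2 × 6 = 82 mmHg.

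- 100 to 81 mmHg: the fall is 19 mmHg (19%). Appendix 3 is met (81 < 82); SAP 10.3 is not (19 < 20).
- 105 to 85 mmHg: the fall is 20 mmHg (20 / 105 = 19%). SAP 10.3 is met; Appendix 3 is not (85 > 82, and 19% is below 30%).

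These examples take the same-day starting value as baseline. SAP 5.7 uses the study baseline for the up-dosing period, which is a further choice that the table must state.

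**The case against.** The strongest reply is that hypotension after an AR101 dose already has routes into tables, and this largely stands. Under Appendix 3, reduced blood pressure after allergen exposure can by itself make anaphylaxis likely. SAP 5.7.2 tabulates anaphylaxis for each study period by maximum severity, and the severe stage includes hypotension. SAP 4.6.1 sets out when an abnormal vital sign is reported as an adverse event. SAP 5.3 summarizes epinephrine use at the IDED and epinephrine episodes during up-dosing. A reader might infer that dose-related hypotension is never tabulated; these routes show that the documents do not support that.

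Each route nevertheless needs a diagnosis, a report or a treatment. Reactions at in-clinic AR101 dosing are recorded as allergic signs and symptoms (SAP 4.6.1), and the symptom-severity endpoint in SAP 4.5.3 covers food challenges only. A measured fall that nobody labels therefore remains outside the tables.

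A second reply is that serial post-dose readings do not belong in by-visit tables of change from study baseline. That is fair. It supports a separate block, as was done for the food challenges, but not the absence of one.

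A third is that the PCSV flag and Appendix 3 serve different purposes, one a general screen and the other a diagnostic criterion, and need not agree. This stands. Their disagreement is not an error, only a reason to name the flag used.

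A fourth is that the volume of readings says nothing about consequence, and that Protocol 3.3.2 expects severe allergic symptoms in under 1% of subjects. This also stands.

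**Conclusion.** Post-dose pulse and blood pressure at AR101 up-dosing visits enter no vital-sign summary and no PCSV count. This follows from a stated exclusion rather than a missing detail; it is narrower than Protocol 11.4.4.2 and SAP 5.7, and SAP 1.2.3 does not declare it. The consequence is limited to measured changes not captured as anaphylaxis, an adverse event or epinephrine use. The affected data amount to about 40 to 80 readings per completing subject. The documents give no rate from which to estimate how many falls would go unsummarized.

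Two further inferences go too far. One is that IDED readings are certainly lost: the text leaves their status open. The other is that these readings are taken specifically to detect hypotension: the SAP says only safety monitoring.

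**What to change.** Add a third block to SAP 5.7.4 for AR101 up-dosing visits, parallel to the food-challenge block, giving:

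- change from the same-day pre-dose value in pulse and blood pressure, by AR101 dose level and arm;
- number (%) of subjects with a post-dose PCSV, by arm.

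State whether week 4 IDED post-dose readings belong to this block or to the main PCSV count. State which low-systolic flag the table uses (SAP 10.3 or Protocol Appendix 3), or report both, and against which reference value. The choice concerns tabulation only and implies nothing about clinical management. Record the departure from Protocol 11.4.4.2 in SAP 1.2.3 if any part of the exclusion is kept.

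The cost is one or two extra tables. The readings are already planned, and the food-challenge block gives a layout to follow.
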